7.4.2 Modification of Study Therapy

Summary:

The following will be provided by cohort.

- Number (%) of subjects with dose delay, omission and discontinuation along with the reason
- Number(%) of subjects with dose reduction along with the reason
- Infusion interruptions
 - Number (%) of subjects with at least one infusion interruption along with the reason
 - Number of infusion interruptions per subject
 - Number (%) of subjects with at least one IV infusion rate reduction along with the reason

Listing:

- All relevant information on dose modification listed above

Category	Value
1	Very High
2	Very Low
3	Very Low
4	Very Low
5	Medium
6	High
7	Very Low
8	Very Low
9	Very Low
10	Very Low

7.5 Safety

Safety analyses will be performed primarily on All Treated Subjects and presented by treatment (“as treated”) and overall. In addition, SAE analyses will be produced using All Enrolled Subjects.

Adverse events (AEs) will be coded according to the most current version of MedDRA and be graded using the NCI Common Terminology Criteria for Adverse Events (CTCAE) version 4.03. Drug-related AEs are those events with relationship to study drug “Related” as recorded on the CRF. If the relationship to study drug is missing, the AE will be considered as drug-related. Serious adverse events consist of AEs deemed serious by the Investigator and flagged accordingly in the CRF and clinical database. Adverse events leading to study drug discontinuation are AEs with action taken = “Drug was discontinued”. Adverse events leading to dose delay are AEs with action taken = “Dose was delayed”.

Listing of adverse events will include all enrolled subjects as SAEs and deaths are collected pretreatment. Summaries of adverse events will include events occurring from the date of first study medication and for up to 60 days (inclusive) after the last dose of study drug for Part 1 and 2 and up to 100 days (inclusive) after the last dose of study drug for Part 3 and 4. Listing of serious adverse events will include all enrolled subjects as SAEs and deaths are collected pretreatment. Listing of non-serious adverse events will include all treated subjects.

When reporting adverse events by CTC grade, summary tables will be provided based on the event with worst CTC grade (independent of relationship to study medication). Subjects will only be counted (1) once at the preferred term (PT) level, (2) once at the system organ class (SOC) level, and (3) once in the ‘Total subject’ row at their worst CTC grade, regardless of SOC or PT.

The analysis of laboratory results will be based on All Treated Subjects. Laboratory results will be categorized according to NCI CTCAE (version 4.03) grade. Baseline is defined as the last non-missing measurement prior to or on the first treatment’s dosing date and time. Summaries of laboratory results include baseline and post-baseline results up to 60 days (inclusive) after the last dose of study drug for Part 1 and 2 and up to 100 days (inclusive) after the last dose of study drug for Part 3 and 4 for subjects who are off treatment.

For retreated subject in Part 3 and 4, the initial off-treatment period is included in all safety analysis as if the retreated subject were still on treatment in that period of time.

For the analyses (during original assigned treatments) of subjects treated with the combination therapy extension option in Part 2, all the safety assessment will be truncated at the first dose date of the combination therapy. All others will follow regular counting rules. For the analysis of subjects treated with the combination therapy extension option during the combination period, all the safety assessments will be counted from the first dose of combination therapy and up to 100 days after last dose (optional analyses).

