1.3 Objectives(s)

1.3.1 Primary Objectives

To assess the safety and tolerability of BMS-986183 administered as monotherapy and in combination with nivolumab in subjects with HCC.

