In BMS-986183 dose expansion (Part 2) only, subjects who have disease progression on BMS-986183 monotherapy will be able to receive combination treatment (their current BMS-986183 dose + flat dose of nivolumab, provided that this combination dose has been found to be safe from BMS-986183 and nivolumab dose escalation [Part 3]). This combination therapy option is not applicable during BMS-986183 dose escalation (Part 1). Eligible subjects may receive the combination option after careful evaluation and discussion with the BMS Medical Monitor to determine whether the benefit/risk ratio supports administration of further study therapy. Subjects meeting criteria for retreatment will be treated up to approximately 1 year (17 cycles, with 21 days/cycle) with a dose regimen of the combination of BMS-986183 and nivolumab dose escalation (Part 3). Such subjects must meet the eligibility criteria for receiving the combination of BMS and nivolumab as specified in Table 5.1-3.

If subjects in BMS-986183 dose expansion (Part 2) agree to receive the combination therapy, they must consent to a mandatory biopsy at clinically documented disease progression (see Section 3.3.1). In addition, subjects must wait at least 21 days since their last dose of BMS-986183 before receiving the combination therapy option, but they must receive their first dose of combination therapy within 6 weeks of their last study drug administration. These subjects will follow the assessment schedules in Table 5.1-3 and Table 5.5.1-3.

Subjects who agree to receive the combination therapy will be included in the main analysis up to and including disease progression. After disease progression, subjects who agree to receive the combination therapy will also be analyzed in a subanalysis.

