Clinical Complaints		Х				See note in Table 5.1-1; only if subject entered survival FU.		
Monitor for Nonserious Adverse Events		X	X	X		From first dose of study drug until a total of 100 days post discontinuation of dosing or subject's participation in the study if the last scheduled visit occurs at a later time. See Section 5.3.		
Monitor for SAEs	Х	Х	X	Х		From the time of consent until a total of 100 days post discontinuation of dosing. See Section 5.3.		
Clinical Drug Supplies								
Dose Level Assignment	X					At the completion of Day 0 procedures and eligibility determined.		
BMS-986183 Administration		X				The start and stop time of the study drug infusion should be documented (start of drug infusion = 0 hour). See Section 4 for administration details. Subjects in BMS-986183 dose escalation (Part 2) Combination Therapy Extension Option must receive their first dose of combination therapy within 6 weeks of their last study drug administration.		

Procedure ^a	Day 0 b,c	C1 and Beyond D1	ΕΟΤ	FU (30, 60, and 100 Days after Last Dose) (30- and 60-day FU: ± 5 days) (100-day FU: ± 10 days)	Survival FU ^d (±2 weeks)	Notes	
Nivolumab Administration		X				BMS-986183 is infused first followed by nivolumab. See Section 4 for administration details. See Section 3.1.1.2 for observation times. The start and stop time of the study drug infusion should be documented (start of drug infusion = 0 hour). Subjects in BMS-986183 dose escalation (Part 2) Combination Therapy Extension Option must receive their first dose of combination therapy within 6 weeks of their last study drug administration.	
Other							
Survival FU					X ⁱ		

^a In the event that multiple procedures are required at a single timepoint, the ECG may be obtained up to 15 minutes earlier, vital signs may be obtained up to 10 minutes earlier or later, and clinical laboratory sample may be obtained up to 5 minutes earlier than the nominal PK timepoint, ensuring the PK samples can be collected on time.

Abbreviations: C = cycle, D = day; FU = follow=up; PE = physical examination; T3 = triiodothyronine; T4 = thyroxine; TSH = thyroid stimulating hormone.

^b Day 0 is first day of assessment for either retreatment or combination therapy extension.

^c For BMS-986183 dose expansion (Part 2), BMS-986183 and nivolumab dose escalation (Part 3), and BMS-986183 and nivolumab dose expansion (Part 4), if the Day 0 and C1 visits occur on the same day, then only a single examination or procedure is needed.

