8.2 Populations for Analyses

- All Enrolled Subjects: All subjects who sign an ICF.
- All Treated Subjects: All subjects who receive at least one dose of study drug.
- PK Subjects: All subjects who receive at least one dose of BMS-986183 monotherapy (or BMS-986183 and nivolumab combination therapy) and have available serum and/or plasma concentration data.
- Biomarker Subjects: All treated subjects for whom pharmacodynamic measurements are available at both baseline and at least one other time after treatment.
- Immunogenicity (ADA) Population: all treated subjects who had baseline and at least 1 post-treatment immunogenicity assessment
- ECG Evaluable Population: all treated subjects who had a baseline ECG and at least 1 on-study ECG.
- Response Evaluable Population: all treated subjects who had baseline tumor measurement and at least one other tumor measurement after treatment, clinical progression, or death prior to the first on-treatment tumor assessment.

All subjects who receive study drug will be included in the safety data set.

All available data from subjects who receive BMS-986183 monotherapy (or BMS-986183 and nivolumab combination therapy) will be included in the PK data set.

All available data from subjects for whom pharmacodynamic measurements are available at baseline and at least one other time will be included in the pharmacodynamic data set.

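### The SAP makes the safety summary of the Part 2 combination extension optional, so adverse events on the combination there may appear only in listings

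*SAP*

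**What the plan says.** Protocol 3.1.2.1 lets Part 2 subjects who progress on monotherapy receive the combination, and divides their analysis in two. First: "Subjects who agree to receive the combination therapy will be included in the main analysis up to and including disease progression". Then: "After disease progression, subjects who agree to receive the combination therapy will also be analyzed in a subanalysis". No condition is attached to the second sentence, and no type of data is named.

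SAP 7.5 gives the safety rule. For the originally assigned treatment, "all the safety assessment will be truncated at the first dose date of the combination therapy". For the combination period, safety would be counted from the first combination dose "up to 100 days after last dose (optional analyses"); the parenthesis marks that analysis as optional.

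The primary objective (protocol 1.3.1) is "To assess the safety and tolerability of BMS-986183 administered as monotherapy and in combination with nivolumab in subjects with HCC". Protocol 8.2 adds: "All subjects who receive study drug will be included in the safety data set". In the schedule for retreatment and the extension (protocol 5.1, Table 5.1-3), non-serious AEs are collected "From first dose of study drug until a total of 100 days post discontinuation of dosing".

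**The concern.** The protocol states an analysis of the extension as something that will be done. The SAP leaves the safety part of it to later choice. The study is open label, so that choice could be made after the events are known, and it concerns safety of the combination, which is a primary endpoint domain.

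The events at stake are AEs, SAEs, AEs leading to discontinuation and laboratory shifts that arise on the combination in these subjects. Their safety profile may also differ from that of the planned combination cohorts. They have progressed after at least one prior systemic regimen and have already been exposed to BMS-986183, whereas Part 4 admits only subjects with no prior systemic therapy. The planned pretreated combination group is Part 3, with about 21 subjects.

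**Working it through.** The plan gives no figure for this point, so the check is a trace. Take an event that starts after the first combination dose in a Part 2 extension subject, and ask which SAP outputs would hold it.

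| SAP output | Is the event included? |
|---|---|
| Part 2 summaries of SAEs, AEs, AEs leading to discontinuation and laboratory grades (7.5.2 to 7.5.4, 7.5.8) | No: removed by the truncation in 7.5 |
| Part 3 and Part 4 summaries | No rule moves these subjects there; 6.2 lists four parts and has no extension category |
| Combination-period summary (7.5) | Counting window defined, production optional |
| All-deaths summary (7.5.1) | A death may be counted: no time window, and truncation is not mentioned |
| Disposition (7.3.1) and dose modification (7.4.2) | A discontinuation may be counted: truncation is not mentioned |
| By-subject listings (7.5.1 to 7.5.4, 7.5.8) | Yes |

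So for AEs, SAEs, AEs leading to discontinuation and laboratory shifts, the only summary written for the period is the optional one. The same part of SAP 7.5 treats retreated Part 3 and 4 subjects differently: even their initial off-treatment interval is kept in all safety analyses.

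**Cut-offs.** The protocol ends the main analysis at disease progression; the SAP ends it at the first combination dose. An event between those two dates is outside the main analysis under the protocol and inside the main safety analysis under the SAP.

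**How many subjects.** Inputs (SAP 2.1): about 50 in Part 2, 21 in Part 3 and 50 in Part 4. The documents give no crossover rate, so I show the range. With *x* subjects crossing over, their share of all combination-exposed subjects is *x* / (21 + 50 + *x*) = *x* / (71 + *x*).

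- *x* = 0: 0 / 71 = 0%
- *x* = 25 (assumption: half of Part 2): 25 / 96 = 26%
- *x* = 36 (assumption: all cross over, and Part 2 enrols the simulated average for response rates no better than 5%, SAP section 5): 36 / 107 = 34%
- *x* = 50 (assumption: all of Part 2 crosses over): 50 / 121 = 41%

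Any *x* above 21 would exceed the planned size of Part 3.

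**The case against.** **The protocol does not promise a safety table.** A reader might infer that the SAP withdraws a promised safety summary. The text does not go that far: the subanalysis sentence names no data type, and progression is an efficacy landmark, so an efficacy subanalysis might be what was meant. This stands as a limit on the claim. It does not remove the problem, because the sentence is unrestricted and combination safety is part of the primary objective.

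**Deaths and discontinuations need not vanish.** A reader might also infer that every outcome on the extension drops out of all tables. The documents do not support that. The all-deaths summary has no window, the disposition and dose-modification tables carry no stated truncation, and the listings cover all recorded events. No data are lost. What remains exposed is the set of AE, SAE, AE-leading-to-discontinuation and laboratory summaries.

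**The analysis may be specified elsewhere.** SAP section 9 defers the full list of outputs to a Data Presentation Plan, which is not among the documents, and some SAP text is redacted or absent. The tables may be planned there. Nothing visible in the SAP requires them, and the visible text says optional.

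**Parts 3 and 4 are the designed source of combination safety.** That is true: they have required tables, and extension subjects are supplementary. Truncating these subjects out of the monotherapy analysis is also sound. Neither fact explains why the remaining period should be summarised only at discretion.

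**Uptake may be low.** Entry needs progression, a combination dose found safe in Part 3, combination eligibility, medical monitor discussion, a biopsy at progression, and a first combination dose within a set interval. This stands: 41% is a ceiling and should not be read as an expectation.

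**Conclusion.** The point holds for AEs, SAEs, AEs leading to discontinuation and laboratory shifts on the combination in Part 2 extension subjects. Followed as written, the SAP can leave them in by-subject listings only. It does not hold as a claim that deaths or general discontinuations disappear, or that the protocol expressly promised a safety table.

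The size is unknown: 0 to about 50 subjects, or 0 to 41% of those exposed to the combination, on the assumption that the whole of Part 2 is the ceiling and Parts 3 and 4 enrol as planned. The mismatch matters at any non-zero uptake. The conclusion rests on the SAP text available; a Data Presentation Plan that already requires these tables would reduce the point to aligning the wording.

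**What to change.** In SAP 7.5, delete the parenthesis that makes the combination-period analysis optional. Then:

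- Commit, if any subject enters the extension, to summaries of AEs, SAEs, AEs leading to discontinuation and laboratory results from the first combination dose to 100 days after the last dose.
- Show them separately from Part 2 monotherapy and from Parts 3 and 4.
- State in SAP 7.5.1 how deaths during the extension are counted in the death summary.
- Reconcile the protocol cut-off (disease progression) with the SAP cut-off (first combination dose), and say in which analysis events between the two dates belong.

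The data are already collected to 100 days and the counting window is already written. The cost is a few more tables, possibly with few subjects in them.

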7.5.1 Deaths

Summary:

Deaths will be summarized by treatment:

- All deaths, reasons for death
- Deaths within 60 days of last dose received, reasons for death
- Deaths within 100 days of last dose received, reasons for death

Listing:

All recorded deaths for All Enrolled subjects will be listed by subject.

7.5.2 Serious Adverse Events

Summary:

Serious adverse events will be summarized by treatment:

- Overall summary of SAEs by worst CTC grade (grade 1, 2, 3, 4, 5, unknown) presented by SOC/PT
- Overall summary of drug-related SAEs by worst CTC grade (grade 1, 2, 3, 4, 5, unknown) presented by SOC/PT
- Overall summary of SAEs by worst CTC grade (any grade, grade 3-4, grade 5) presented by SOC/PT.
- Overall summary of drug-related SAEs by worst CTC grade (any grade, grade 3-4, grade 5) presented by SOC/PT.

Listing:

- All recorded SAEs for All Enrolled Subjects.

7.5.3 Adverse Events

Summary:

Adverse events will be summarized by treatment:

- Overall summary of any AEs by worst CTC grade (grade 1, 2, 3, 4, 5, unknown) presented by SOC/PT
- Overall summary of any AEs by worst CTC grade (any grade, grade 3-4, grade 5) presented by SOC/PT.
- Overall summary of drug-related AEs by worst CTC grade (grade 1, 2, 3, 4, 5, unknown) presented by SOC/PT.
- Overall summary of drug-related AEs by worst CTC grade (any grade, grade 3-4, grade 5) presented by SOC/PT.
- Overall summary of any non-serious AEs presented by SOC/PT.

The analyses will be conducted using the 60 days safety window.

Listing:

- All recorded Adverse Events for All Treated Subjects.
- All drug-related Adverse Events for All Treated Subjects.

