All subjects will enter the safety follow-up period once the decision is made to discontinue the subject from treatment (eg, at end of treatment [EOT]).

After the EOT visit, all subjects will be evaluated for any new AEs for a total of 60 days after the last dose of study drug for BMS-986183 dose escalation (Part 1) and BMS-986183 dose expansion (Part 2) and for a total of 100 days after the last dose of study drug for BMS-986183 and nivolumab dose escalation (Part 3) and BMS-986183 and nivolumab dose expansion (Part 4). Follow-up visits should occur at 30 and 60 days (\pm 5 days) after the last dose. Subjects in BMS-986183 and nivolumab dose escalation (Part 3) and BMS-986183 and nivolumab dose expansion (Part 4) will have an additional visit at 100 days (\pm 10 days) after the last dose. All subjects will be required to complete their clinical safety follow-up visits regardless of whether they start new anti-cancer therapy, except those subjects who withdraw consent for study participation.

Subjects who develop toxicity requiring discontinuation of treatment will enter the safety follow-up period. The subject should be seen at least every 30 days, until the AE has resolved to baseline, stabilized, or been deemed irreversible.

Survival Follow-up Period

After completion of the safety follow-up period, all subjects will enter the survival follow-up period. All subjects will be followed by telephone contact, office visit, or documented clinic visit every 12 weeks (\pm 2 weeks) from his/her last dose of study drug for 6 months until progression or death. Both response and survival follow-up periods will occur simultaneously during the 6-month follow-up period. The duration of this period is up to 6 months following the subject's last dose of study drug. Subjects in the survival follow-up period who progress will be eligible to receive anti-cancer therapy as appropriate.

Retreatment during Survival Follow-up (Parts 3 and 4 only)

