Viral biomarkers (for HCV and HBV)		Х					For HCV infected, HCV RNA on treatment For HBV infected, HBV DNA on treatment
Troponin T or I	Х	Х			Х	Х	The same evaluation (assay) must be performed throughout the study
Pregnancy Test	Х	Х					For WOCBP only; see Section 5.3.2
Whole blood sample for ADME		Х					See Section 5.7.3
PK and Immunogenicity Assessments S	ee Section 5.5.						
Biomarker Assessments See Section 5.6.							
Tumor Sample	Х						See Section 3.3.1.
Tumor Assessment Tumor Imaging (See Section 5.3.1)	х						Baseline must be within approximately 30 days of C1D1 Scans must be de-identified. See Section 5.3.1.
Concomitant Treatments		X	X	X	X	X	Medications administered within 4 weeks of dosing and all anti-viral medications taken for any length of treatment through 60 days post-study drug discontinuation for BMS-986183 dose escalation (Part 1) and BMS-986183 dose expansion (Part 2) and for 100 days after the last dose of study drug for BMS-986183 and nivolumab dose escalation (Part 3) and BMS-986183 and nivolumab dose expansion (Part 4).

Procedure ^a	Screening Visit D-28 to D-1	C1D1	C1D2	C1D4 ^b	C1D8	C1D15	Notes
Adverse Event Reporting		•					
Clinical Complaints	Х						Clinical complaints related to the disease under study must be collected within 14 days of the first dose of study drug.
Monitor for Nonserious Adverse Events							BMS-986183 dose escalation (Part 1) and BMS-986183 dose expansion (Part 2): From first dose of study drug until a total of 60 days post discontinuation of dosing or subject's participation in the study if the last scheduled visit occurs at a later time.
		X	Х	X	Х	Х	BMS-986183 and nivolumab dose escalation (Part 3) and BMS-986183 and nivolumab dose expansion (Part 4): From first dose of study drug until a total of 100 days post discontinuation of dosing or subject's participation in the study if the last scheduled visit occurs at a later time.
							See Section 5.3.
Monitor for SAEs							BMS-986183 dose escalation (Part 1) and BMS-986183 dose expansion (Part 2): From the time of consent until a total of 60 days post discontinuation of dosing.
	Х	Х	Х	Х	Х	Х	BMS-986183 and nivolumab dose escalation (Part 3) and BMS-986183 and nivolumab dose expansion (Part 4): From the time of consent until a total of 100 days post discontinuation of dosing. See Section 5.3.
Clinical Drug Supplies		l		l	l		
Dose Level Assignment	Х						At the completion of screening procedures and eligibility determined

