4 ENDPOINTS

4.1 Primary Endpoints

Primary endpoints will include incidence of AEs at their worst grade, SAEs at their worst grade, AEs leading to discontinuations, deaths, and frequency of laboratory test toxicity grade shifting from baseline. Safety will be evaluated from the time that the subject signs the informed consent and for up to 60 days after the last dose of study drug for BMS-986183 monotherapy dose

escalation period (Part 1) and BMS-986183 monotherapy dose expansion period (Part 2) and up to 100 days after the last dose of study drug for BMS-986183 and nivolumab combination therapy dose escalation (Part 3) and BMS-986183 and nivolumab combination therapy dose expansion (Part 4). AEs and laboratory values will be graded according to the National Cancer Institute (NCI) Common Terminology Criteria for Adverse Events (CTCAE) version 4.03.

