6.1.2 Post-baseline period

- On-treatment AEs will be defined as AEs with an onset date and time on or after the date and time of the first dose of study treatment (or with an onset date on or after the day of first dose of study treatment if time is not collected or is missing). For subjects who are off study treatment, AEs will be included in summaries if event occurred within a safety window of 60 days after the last dose of study for BMS-986183 monotherapy dose escalation period (Part 1) and BMS-986183 monotherapy dose expansion period (Part 2) and of 100 days after the last dose of study drug for BMS-986183 and nivolumab combination therapy dose escalation (Part 3) and BMS-986183 and nivolumab combination therapy dose expansion (Part 4).
- On-treatment evaluations (laboratory tests, pulse oximetry and vital signs) will be defined as evaluations taken after the day (and time, if collected and not missing) of first dose of study treatment. For subjects who are off study treatment, summaries will include measurements

within a safety window of 60 days after the last dose of study for BMS-986183 monotherapy dose escalation period (Part 1) and BMS-986183 monotherapy dose expansion period (Part 2) and of 100 days after the last dose of study drug for BMS-986183 and nivolumab combination therapy dose escalation (Part 3) and BMS-986183 and nivolumab combination therapy dose expansion (Part 4).

- Tumor assessments will be slotted in the post-baseline period if assessments are after start of the treatment date.

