7.5.6 Multiple Events

Analyses that take into account the multiple occurrences of a given adverse event will be conducted. To prepare these analyses, the CRF data will be processed according to standard BMS algorithms⁵ in order to collapse adverse event records into unique records based on the preferred term. This data will be presented as the rate per 100 person-years of exposure. These analyses will take into account all on-treatment events (allowing more than 1 event per subject) and the total exposure time. The person-year exposure will be computed as the sum over the subjects' exposure expressed in years where the exposure time is defined as

- Date of last dose of study treatment - date of first dose of study treatment + 61 days (+ 101 days for Part 3 and 4), for subject who are off study treatment and were followed for at least 60 days (100 days for Part 3 and 4) after last dose of study treatment.
- Last known date alive- date of first dose of study treatment + 1, for subjects who are still on-treatment or who are off study treatment and were followed less than 60 days (or 100 days for Part 3 and 4) after last dose of study treatment.

When specified the 95%CI of the rate per 100 person-year of exposure will be derived using normal approximation and variance estimation proposed in Cook and Lawless⁶ (optional).

Summary:

The following summary tables will be provided for each treatment:

- Total number and rate (exposure adjusted) of occurrences for all AEs occurring in at least 5% of the subjects treated per study treatment.

Listing:

- Listing displaying the unique instances of all AEs, i.e., after duplicates have been eliminated and overlapping and contiguous occurrences of the same event (i.e. same PT) have been collapsed will be provided.

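### SAP 7.5.3 applies a 60-day window to its AE summaries in every Part, while SAP 6.1.2 and 7.5 set 100 days for Parts 3 and 4

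*SAP*

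**What the plan says.** SAP 7.5.3 (Adverse Events) calls for five summaries: all AEs by worst grade in two layouts, drug-related AEs by worst grade in two layouts, and non-serious AEs by system organ class and preferred term. Directly after the list it states: "The analyses will be conducted using the 60 days safety window". No Part is named, and the window is not described as common or supplementary.

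Two other SAP sections set the window for the same kind of output:

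- **SAP 6.1.2**, for subjects off treatment in Parts 1 and 2: "AEs will be included in summaries if event occurred within a safety window of 60 days after the last dose of study". For the combination Parts it continues: "and of 100 days after the last dose of study drug for BMS-986183 and nivolumab combination therapy dose escalation (Part 3".
- **SAP 7.5**, the parent section, has AE summaries run from first study medication "for up to 60 days (inclusive) after the last dose of study drug for Part 1 and 2 and up to 100 days (inclusive"; the 100 days apply to Parts 3 and 4.

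Other places use the same split by Part but do not set the window of these tables. SAP 4.1 evaluates the primary safety endpoints in the combination Parts up to "100 days after the last dose of study drug for BMS-986183 and nivolumab combination therapy dose escalation (Part 3" and Part 4. SAP 7.5.6 builds exposure time with "61 days (+ 101 days for Part 3 and 4), for subject who are off study treatment". Protocol 3.1 evaluates subjects for new AEs "and for a total of 100 days after the last dose of study drug for BMS-986183 and nivolumab dose escalation (Part 3" and Part 4. Protocol Table 5.1-1 collects non-serious AEs in those Parts as follows: "From first dose of study drug until a total of 100 days post discontinuation of dosing".

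**The concern.** A programmer reading 7.5.3 alone would cut all five tables at day 60 in every Part. A programmer following 6.1.2 or 7.5 would cut Parts 3 and 4 at day 100. Either reading can be defended, as the more specific sentence or as the general rule, and they give different tables for the combination Parts.

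These are not peripheral tables. Incidence of AEs at worst grade is a component of the primary endpoint, and 7.5.3 is where it is reported. The combination Parts are where late onset is of most interest: Protocol 4.5.2.2 defines immune-mediated adverse reactions over 100 days from last dose. Under the literal reading, events first seen between the day-60 and day-100 visits would be collected and then left out of the all-AE and drug-related tables. Tables within one report would also disagree about the same event.

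**Working it through.** No stated figure needs reproducing. The check is a comparison of the rules, followed by a trace of what each one does.

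**1. Window for AE summaries, in days after last dose**

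| Place | Parts 1 and 2 | Parts 3 and 4 | Sets the window for AE summaries? |
|---|---|---|---|
| SAP 7.5.3 | 60 | 60 (no exception) | Yes, its five summaries |
| SAP 6.1.2 | 60 | 100 | Yes |
| SAP 7.5 | 60 | 100 | Yes |
| SAP 4.1 | 60 | 100 | No, endpoint evaluation period |
| SAP 7.5.6 | 60 (+61 in the formula) | 100 (+101 in the formula) | No, separate rate table |
| Protocol 3.1 | 60 | 100 | No, AE evaluation |
| Protocol Table 5.1-1 | 60 | 100 | No, AE collection |

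The rules agree for Parts 1 and 2. For Parts 3 and 4 the direct conflict is between 7.5.3 on one side and 6.1.2 and 7.5 on the other.

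**2. An event on day 80 after last dose in Part 3 or 4, with 7.5.3 read literally**

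- Serious event: it is in the SAE tables, because 7.5.2 states no window and so takes 100 days from 7.5. It is not in the all-AE table of 7.5.3.
- Non-serious, non-laboratory event: it is in none of the 7.5.3 summaries. It reaches another worst-grade table only if it led to discontinuation (7.5.4) or dose modification (7.5.5), or if its term is on the sponsor's special-interest list (7.5.7). New events this long after the last dose will rarely lead to a dose modification.
- Outputs that still hold late events: the listings, laboratory grading to 100 days (7.5 and 7.5.8), the 100-day death summary (7.5.1), and the exposure-adjusted rates of 7.5.6 for AEs seen in at least 5% of subjects.

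**3. Size**

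- Planned subjects in the affected Parts: 21 + 50 = 71, and 71/151 = 47.0%.
- Omitted days: 100 − 60 = 40, which is 40/100 = 40% of the post-dose window.
- The summary window starts at first dose. With k doses every 21 days and no delay its length is 21(k − 1) + 100 days, so the omitted share of the whole window is:
  - k = 1: 40/100 = 40%
  - k = 4: 40/(63 + 100) = 40/163 = 24.5%
  - k = 17: 40/(336 + 100) = 40/436 = 9.2%

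All of these are shares of time, not of events. A worst-grade row changes only for a subject who is off treatment, is followed past day 60, and has an onset on days 61 to 100 that is a new term or exceeds the earlier worst grade. The documents give no basis for that count. Retreated subjects in Parts 3 and 4 are less exposed, because 7.5 already treats the gap before retreatment as on-treatment time.

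**The case against.** The best case for leaving this alone is that 7.5.3 is the single outlier. The endpoint section, the definition of on-treatment AEs, the parent safety section and the exposure formula all use 100 days for Parts 3 and 4. The sentence refers to the 60-day window as something already defined, and 6.1.2 defines such a window for Parts 1 and 2 only. It may therefore be an incomplete cross-reference rather than a competing rule. The study tests no formal hypothesis, the tables are descriptive and can be rerun, and collection is unaffected. SAP section 9 also defers the full list of analyses to a Data Presentation Plan, which was not available and may settle the window table by table.

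Much of this stands. The sentence may well be an oversight, it cannot be shown that the final tables will be cut at day 60, and the 40% overstates the share of the whole summary window for anyone who received several doses. The protocol's 100-day immune-mediated definition gives context only, since no visible SAP table is built on it. None of this removes the conflict. The SAP gives two windows for the same tables and no order of precedence. Where it wants two windows it shows both, as for deaths in 7.5.1. Where the window varies by Part it says so, as in 7.5.6. If a common 60-day window was intended, the text needs to state that.

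**Conclusion.** The concern holds. As written, SAP 7.5.3 contradicts 6.1.2 and 7.5 for Parts 3 and 4, and following it would give all-AE, drug-related and non-serious AE tables that omit onsets on days 61 to 100 after last dose. These tables report a primary-endpoint component, so the point should be fixed, although no data are lost and Parts 1 and 2 are unaffected. Exposure to the conflict is up to about 71 of 151 planned subjects, assuming Parts 3 and 4 enrol as planned. The number of table entries that would change is unknown. The conflict itself is certain from the text. Its effect on the final report depends on which rule is programmed.

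**What to change.** Replace the sentence in SAP 7.5.3 with: *Analyses use the 60-day window for Parts 1 and 2 and the 100-day window for Parts 3 and 4, as in Sections 6.1.2 and 7.5.* Leave the rule in 7.5 for Part 2 subjects who take the combination extension as it is. If a common 60-day table is wanted for comparing Parts, add it and label it supplementary for Parts 3 and 4. Check that the Data Presentation Plan carries the same windows.

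The cost is one sentence in the SAP. No new data are needed, because the protocol already evaluates and collects AEs to 100 days in these Parts.
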